#### 8.1.1. sUA Levels

Serum uric acid (sUA) is one of the key parameters to efficacy endpoints.

Proportion of subjects meeting pre-specified criteria at Day 84 (Visit 8) is derived as:  $100\% * \text{number of subjects meeting criteria} / \text{number of all subjects at Day 1 (Visit 4)}$ , where dropout subjects will be considered as not meeting the criteria.

Change and percent change in sUA from Baseline (Visit 4) at each visit are derived as:

- Change = (Value - Baseline)
- Percent change =  $100\% * (\text{Value} - \text{Baseline}) / \text{Baseline}$

Missing sUA values will be imputed with Last Observation Carried Forward (LOCF) method.

#### 8.1.2. Antiflare Activities

For this study, a gout flare is defined as an episode of subject-reported acute articular or bursal pain that occurs at rest and is typical of past gout attacks. In addition, both of the following criteria must be met: the intensity of pain at rest must be  $\geq 4$  on an 11-point numerical rating scale, and the pain must be determined by the patient and/or the Investigator to require anti-inflammatory/analgesic treatment (i.e. rescue medication). Finally, at least 2 of 3 possible joint symptoms (swelling, warmth, or tenderness) must be present, and at least 1 of the following must be present: rapid onset of pain, decreased range of joint motion, or joint redness.

To assess occurrence of gout flare, parameters related to joint pain will be evaluated by the data collected through eDiary, but in the case of rescue medication, data collected by eCRF will also be evaluated:

- When evaluating administration of rescue medication collected through eDiary, the date of rescue medication administration, eDiary entry date, should match with the date of the reported joint pain.
- When using concomitant medication data collected by eCRF, the date of reported joint pain should be within start and stop dates of rescue medication administration.

If subjects report to have joint pain continuously in several days or time, it will be counted as one event.

Gout flare rate will be calculated as: number of episodes of gout flare in a specific period (or during the study) / number of subjects, for each treatment group. Summaries of gout flare rate will be produced for 1) all subjects and 2) subjects with sUA < 6.0 mg/dL at Day 84 (Visit 8).

Proportion of subjects with episodes of gout flare, i.e. the percentage of subjects experienced gout flare out of all subjects, will be summarized.

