6.0 STUDY DESIGN AND DESCRIPTION

6.1 Study Design

This randomized, double-blind, parallel group, placebo-controlled dose finding study will assess the efficacy in terms of sUA lowering (primary endpoint, <5 mg/dL; secondary endpoint, <6 mg/dL) and the safety and tolerability of LC350189. The study will be conducted at multiple sites in the U.S. in up to 152 subjects. If a subject withdraws from the study, the subject will not be replaced.

Subjects will be randomized 1:1:1:1 (n=38 per group) to the test groups: LC350189 50 mg, LC350189 100 mg, or LC350189 200 mg, or the placebo. Each subject will undergo a screening visit 33 to 26 days prior to the first day of the treatment period (Visit 1); a visit 30 to 23 days prior to the first day of the treatment period to enter a washout period and/or initiate prophylaxis (Visit 2); a visit 9 to 4 day(s) prior to the first day of the treatment period to obtain a blood sample to assess eligibility for randomization based on the inclusion criterion of sUA ≥ 8.0 mg/dL to ≤ 12.0 mg/dL (Visit 3); a treatment period that will include five visits on Day 1, 14, 28, 56, and 84 (Visits 4 to 8); and a follow-up on-site visit approximately 2 weeks (Day 98) after completion of the dosing period (Visit 9). The duration of the study will be up to 19 weeks for each subject.

Eligible subjects receiving ULT will discontinue their ULT and enter a wash-out period starting at Visit 2 prior to receiving study treatment. All subjects will receive gout flare prophylaxis with colchicine 0.6 mg (QD) starting at Visit 2 (between Day -30 to -23) through the end of the treatment period.

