12.4 Determination of Sample Size

Sample size estimation is based on the proportion of subjects meeting target. Calculation of the sample size based on these assumptions is as follows:

[Hypothesis]

$$H_0 : p_t - p_c \leq 0 \text{ vs } H_1 : p_t - p_c > 0$$

$$n = \frac{(Z_\alpha + Z_\beta)^2(p_t(1-p_t) + p_c(1-p_c))}{(p_t - p_c)^2}$$

Where p is the estimated proportion for each group expressed as the proportion of subjects who achieve sUA <5.0 mg/dL at Day 84 (Visit 8), p_t is the proportion of a test group, and p_c is the proportion of a control group. The values Z_α and Z_β represent values of the standard normal distribution that correspond to a type I error rate of $\alpha=0.025$ and a type II error rate of $\beta=0.2$. Evaluable subjects per study group is determined using estimates of $p_t=0.80$ and $p_c=0.47$, and directly computed values of $Z_\alpha=1.96$ and $Z_\beta=0.84$. Assuming a dropout rate of 20%, 38 subjects per study group are needed to assess the efficacy of LC350189 in an evaluable population of 30 subjects per study group.

The size of the control population is based on the FACT trial (Becker et al 2005a), in which a post hoc analysis of sUA at final visit showed sUA <5 mg/dL in 118/249 (47%) patients treated with febuxostat 80 mg.

Power	Alpha, one-sided	P (test)	P (control)	N (per group)	N (Including drop-out 20%)
80%	0.025	0.80	0.47	30	38

Originally, sample size was calculated compared to the active control group in previous protocol versions. Although a major modification is made to eliminate the active control group, the sample size of each test and placebo group is not changed because the proportion of meeting target is very low in the placebo group when referring other studies and sample size calculation comparing to placebo which is less than 10 subjects per group gives insufficient number for dose selection. Therefore, the sample size is not changed upon elimination of the active control group and maintained 30 subjects per group (38 including drop-out rate 20%) to be sufficient for dose selection and exploratory purpose.

The power when compared to placebo group with the current sample size is calculated more than 99% as follows.

Power	Alpha, one-sided	P (test)	P (placebo)	N (per group)	N (Including drop-out 20%)
>99.9%	0.025	0.80	0.1	30	38

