##### 3.2.2. Secondary Endpoint(s)

The secondary endpoints of this study are:

- Proportion of subjects who achieve sUA level of <6.0mg/dL at Day 84 (Visit 8)
- Proportion of subjects who achieve sUA level of <5.0 mg/dL at each visit
- Proportion of subjects with baseline (Visit 4) sUA >10 mg/dL who achieve <5.0 mg/dL at Day 84 (Visit 8)
- Proportion of subjects with baseline (Visit 4) sUA >10 mg/dL who achieve <6.0 mg/dL at Day 84 (Visit 8)
- Proportion of subjects per renal function at baseline (Visit 3) who achieve sUA <5.0 mg/dL at Day 84 (Visit 8)
- Proportion of subjects per renal function at baseline (Visit 3) who achieve sUA <6.0 mg/dL at Day 84 (Visit 8)
- Change and percent change in sUA levels from baseline (Visit 4) at each visit
- Maximum percent reduction in sUA level during treatment
- Ctrough, ss at baseline (Visit 4), Day 14 (Visit 5), Day 28 (Visit 6), Day 56 (Visit 7), and Day 84 (Visit 8)
- Gout flare rate in subjects

- Gout flare rate in subjects with sUA <6.0 mg/dL at Day 84 (Visit 8)
- Proportion of subjects with episodes of gout flare requiring rescue treatment

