## 4. GENERAL STATISTICAL CONSIDERATIONS

### 4.1. Sample Size Determination

Sample size estimation is based on the proportion of subjects meeting target. Calculation of the sample size based on these assumptions is as follows:

$$H_0: p_t - p_c \leq 0 \text{ vs. } H_1: p_t - p_c > 0$$

$$n = \frac{(Z_\alpha + Z_\beta)^2 (p_t(1 - p_t) + p_c(1 - p_c))}{(p_t - p_c)^2}$$

Evaluable subjects per treatment group (n=30) is determined using estimates of proportion of subjects who achieve sUA <5.0 mg/dL at Day 84 (Visit 8), with  $p_t=0.80$  (test group) and  $p_c=0.47$  (control group), and directly computed values of  $Z_\alpha=1.96$  and  $Z_\beta=0.84$ , which correspond to a type I error rate of  $\alpha=0.025$  and a type II error rate of  $\beta=0.2$ .

Assuming a dropout rate of 20%, 38 subjects per treatment group are needed to assess the efficacy of LC350189 in an evaluable population of 30 subjects per treatment group.

Originally, sample size was calculated compared to the active control group in previous protocol versions. Although a major modification is made to eliminate the active control group, the sample size of each test and placebo group is not changed because the proportion of meeting target is very low in the placebo group when referring other studies and sample size calculation comparing to placebo which is less than 10 subjects per group gives insufficient number for dose selection. Therefore, the sample size is not changed upon elimination of the active control group and maintained 30 subjects per group (38 including drop-out rate 20%) to be sufficient for dose selection and exploratory purpose.

In this study, with an overall dropout rate of 20%, a total of 152 subjects, not including those already assigned to the active control group (with febuxostat), will be randomized to 4 treatment groups, 114 subjects to three different test doses of LC350189 (38 subjects to each dose), and 38 subjects to placebo.

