##### **4.4.3. Full Analysis Set**

The Full Analysis Set (FAS) is defined as all randomized subjects that received at least one dose of investigational products (LC350189, febuxostat, or placebo).

The FAS will be applied as the primary population for efficacy analysis, based on treatment that subjects were randomized.

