### 8.1. Analysis of Efficacy Endpoints

The efficacy endpoints of this study are specified in Sections [3.2.1](#), [3.2.2](#), and [3.2.4](#) of this SAP.

All endpoints will be summarized descriptively and will be compared to placebo using descriptive statistics.

Proportions will be analyzed using the Cochran-Mantel Haenszel (CMH) test adjusted by following stratification factors: 1) tophi status at Visit 1, and 2) sUA (level <9.8 mg/dL or  $\geq 9.8$  mg/dL) at Visit 4. The Wald asymptotic 95% confidence limit will be calculated for the risk difference point estimate for pairwise comparisons between each dose group and placebo in pre-specified order of 200 mg versus placebo, 100 mg versus placebo and 50 mg versus placebo; however, if the data suggest and warrant it, the continuity correction adjusting for the difference between the normal approximation and the binomial distribution will be applied. Subgroup analyses of proportions of subjects with sUA level < 5.0 mg/dL (and 6.0 mg/dL as well) will be performed by above stratification factors.

Change and percent change from baseline will be analyzed with an analysis of covariance (ANCOVA) model, including treatment, sUA and tophi strata at screening, and baseline values of the dependent variable as a covariate.

As this is not a rigorous confirmatory trial, no multiplicity adjustment is planned for multiple treatment comparisons or multiple endpoints.

Dropouts will be treated according to non-responder imputation (NRI).

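### The SAP 8.1.2 flare rate has no follow-up term, so in the FAS it favours the arm with more or earlier dropout whenever dropout differs between arms

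*SAP*

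**What the plan says.** SAP 3.2.2 lists "Gout flare rate in subjects" among the secondary endpoints. SAP 8.1.2 defines it, for each treatment group, as "number of episodes of gout flare in a specific period (or during the study) / number of subjects". It is to be shown for all subjects and for those with sUA below 6.0 mg/dL at Day 84. A companion measure, "the percentage of subjects experienced gout flare out of all subjects, will be summarized", uses the same kind of denominator. Neither carries a person-time term, and no at-risk denominator is given for a specific period.

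The primary efficacy set is the FAS, "all randomized subjects that received at least one dose of investigational products" (SAP 4.4.3); SAP section 8 also runs efficacy on the PPS. On leavers, Protocol 6.1 states: "If a subject withdraws from the study, the subject will not be replaced". Protocol 6.4.3 uses data only up to consent withdrawal unless the sponsor indicates otherwise, and flare recording in the eDiary ends at Visit 8 (Protocol 6.1). The planned loss is stated in SAP 4.1: "Assuming a dropout rate of 20%, 38 subjects per treatment group are needed". Protocol 12.4 gives the same figure.

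SAP 8.1 treats dropouts by non-responder imputation, which SAP 8.1.1 and 8.1.3 put into practice for responder proportions. LOCF is specified for sUA and for the exploratory laboratory values. SAP 8.2 gives a sensitivity analysis for the primary endpoint only. None of these rules says how to treat an episode count from a subject who left early.

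On inference, SAP 8.1 says: "All endpoints will be summarized descriptively and will be compared to placebo using descriptive statistics".

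**The concern.** A subject who leaves on Day 14 weighs as much in the denominator as one followed to Day 84, but is observed for one sixth of the time. In effect the leaver is counted as flare-free after leaving. That runs opposite to the sUA response endpoints, where a dropout counts as a failure.

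Antiflare activity is a secondary objective in a trial meant to find a dose. Protocol 4.1 and 6.3 both link the start of urate lowering with flares, so tolerability and retention could differ between the doses and placebo. If they do, part of a difference in the tabulated flare rate would reflect time observed and not flare frequency.

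**Working it through.** **Inputs from the documents.** Treatment period 84 days; 38 subjects per arm; planned dropout 20%; rate = episodes / subjects. **Assumptions, not in the documents.** Dropout by arm, its timing, and the underlying flare rate.

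**1. The plan's only figure that uses dropout.** n = (1.96 + 0.84)² × [0.80×0.20 + 0.47×0.53] / (0.80 − 0.47)² = 7.84 × 0.4091 / 0.1089 = 29.45, rounded up to 30. Then 30 / (1 − 0.20) = 37.5, rounded up to 38, and 4 × 38 = 152. These reproduce. The plan states no figure for the flare rate itself.

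**2. Expected value of the planned rate.** With a constant true rate λ per day and dropout independent of flares, the expected value is λ × mean follow-up. If a proportion d leaves on day t, mean follow-up is (1 − d) × 84 + d × t. If dropout is uniform over 84 days, it is 84 × (1 − d/2). With equal λ in both arms, the ratio is the ratio of mean follow-up and does not depend on λ.

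**3. Planned dropout, same in every arm.** With 20% leaving at Day 14, 28, 42 or 56, mean follow-up is 70.0, 72.8, 75.6 or 78.4 days. That is 83%, 87%, 90% or 93% of 84. Each arm's figure is lower than under full follow-up, but the ratio between arms is 1.00.

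**4. Unequal dropout, identical true rates.**

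| Assumed dropout, arm A vs arm B | Calculation | Planned-formula ratio |
|---|---|---|
| 30% vs 10%, uniform | 0.85 / 0.95 | 0.89 |
| 40% vs 10%, uniform | 0.80 / 0.95 | 0.84 |
| 30% vs 10%, all at Day 14 | 63.0 / 77.0 days | 0.82 |
| 20% at Day 14 vs 20% at Day 42 | 70.0 / 75.6 days | 0.93 |

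The last row shows that timing alone is enough.

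**5. Person-time under the same conditions.** Take an assumed 0.5 flares per 12 weeks and the first row. Per subject: 0.5 × 0.85 = 0.425 and 0.5 × 0.95 = 0.475, ratio 0.89. Per subject-year, both arms give 0.5 / (84 / 365.25) = 2.17, ratio 1.00. A simulation with 38 per arm agreed (0.895 and 1.00).

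**6. If flares cluster early.** Take 30% versus 10% leaving at Day 14, so mean follow-up is 63 and 77 days.
- Half of the flares by Day 28, evenly spread within that time, so one quarter by Day 14: episodes are proportional to 0.7 + 0.3×0.25 = 0.775 and 0.9 + 0.1×0.25 = 0.925. Planned formula 0.84; person-time (0.775/63) / (0.925/77) = 1.02.
- Half by Day 14: 0.85 and 0.95. Planned formula 0.89; person-time (0.85/63) / (0.95/77) = 1.09.

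Person-time is then biased the other way, by less than the planned formula.

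**7. Against sampling error.** At an assumed 0.25 to 1.0 flares per subject per 12 weeks, 38 subjects give 9.5 to 38 episodes per arm. The Poisson standard error of the log ratio is √(2/9.5) = 0.46 to √(2/38) = 0.23. A ratio of 0.89 (log −0.11) is 0.24 to 0.48 standard errors; 0.82 (log −0.20) is 0.44 to 0.87.

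**The case against.** The case for leaving the definition alone has real substance.

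- *The bias is conditional.* The documents plan for 20% dropout with no difference by arm, and equal dropout cancels. This stands: the unequal splits above are scenarios.
- *The plan already has partial protection.* The PPS requires appropriate exposure over 12 weeks, and SAP 4.4.4 allows exclusion of early leavers without Week 12 data. Subjects with Day 84 sUA below 6.0 mg/dL have largely reached Visit 8, unless LOCF values decide membership. This stands in part: both are selected groups, and the FAS remains the primary set.
- *Little hangs on it.* The comparison is descriptive, SAP 8.1 says the trial is not rigorously confirmatory, and no flare test or decision rule is planned. The bias is also below one standard error in the cases shown. This stands, and it limits the weight of the point. A descriptive rate can still mislead when doses are compared.
- *A specific period could mean subjects still at risk.* The SAP neither says so nor rules it out, and the whole-study version has no such protection.
- *Person-time has its own bias.* True if flares cluster early (step 6), and it assumes non-informative dropout. That calls for period-specific rates beside it.

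A reader might also infer that flares driving subjects out would hide flares by the ratios above. The documents do not support that. The figures assume dropout independent of flares, and a subject who leaves because of a flare has usually already contributed it. Flare is not a named withdrawal criterion in Protocol 6.4.3, rescue treatment is available on study (Protocol 9.1.18), and subjects who withdraw are encouraged to continue assessments.

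**Conclusion.** The point holds in conditional form. In the FAS, the SAP 8.1.2 rate favours the arm with more or earlier dropout when dropout differs between arms. For identical, constant true rates, an assumed 30% versus 10% dropout gives 0.89 (uniform over 84 days) or 0.82 (at Day 14) where 1.00 is correct. These sizes rest on assumed splits and on dropout independent of flares; they do not depend on the underlying flare rate.

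Two stronger readings are tempting and should not be drawn. One is that the planned comparison with placebo is biased as it stands: nothing in the documents says that dropout will differ by arm. The other is that every arm's rate is understated: that is so only relative to full follow-up, and only in arms that lose subjects. The primary endpoint and the sample size are untouched.

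**What to change.** In SAP 8.1.2:

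1. Add episodes per subject-time by arm with a 95% CI. Count time, and the episodes within it, from first dose to the earlier of Visit 8 or the end-of-treatment or withdrawal date. Do not use the last diary entry as the end: the documents do not state that entries are daily, and if entries follow events the last one may be a flare day.
2. For period-specific rates, use time at risk, or subjects still at risk, in that period as the denominator. Show these beside the overall rate, because an overall person-time rate can overstate arms with early dropout if flares cluster after treatment starts.
3. Keep episodes per subject as a supporting line.
4. Optionally, fit a Poisson or negative binomial model with log follow-up time as offset. For a descriptive secondary endpoint this is not essential.

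The cost is a few lines of SAP wording and a little extra analysis. First-dose and end-of-treatment dates already enter the compliance derivation in SAP 7.2.2, and Protocol 6.4.3 asks for the consent withdrawal date. The added rate assumes non-informative dropout, which should be stated beside it.

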#### **8.1.3. Other Efficacy Endpoints**

Change from baseline to Day 84 (Visit 8) in HbA1c, in fasting plasma glucose (FPG), and in high-sensitivity C-reactive protein (hs-CRP) will be summarized. Missing values will be imputed with Last Observation Carried Forward (LOCF) method.

Proportions of subjects with HbA1c < 7% at Day 84 (Visit 8) and proportions of subjects with HbA1c <= 6.5% at Day 84 (Visit 8) will be summarized, where dropout subjects will be considered as not meeting the criteria.

Serum concentrations of hypoxanthine and xanthine will be summarized by visit.

### **8.2. Sensitivity Analysis of Efficacy Endpoints**

In sensitivity analysis of the primary efficacy endpoint, using Last Observation Carried Forward (LOCF) method, sUA values at Day 84 (Visit 8) of dropout subjects will be imputed and applied to determine if meeting pre-specified criteria.

## 9. SAFETY ANALYSIS

The purpose of this section is to define the safety endpoints for the study, which consist of adverse events (AEs), clinical laboratory tests, vital sign measurements, and electrocardiograms (ECG), and to describe associated analysis.

All summaries and listings of safety data will be conducted using the Safety Set.

### 9.1. Adverse Events

#### 9.1.1. Definitions

An adverse event (AE) is any undesirable and unintended medical event occurring to a subject in a clinical study, whether or not related to the study products. This includes events from the first study related activity after the subject has signed the informed consent and until post treatment follow-up period as defined in the protocol.

A treatment-emergent AE (TEAE) is defined as any undesirable and unintended medical event after exposure to investigational product or any event already present that worsens in either intensity or frequency after exposure to investigational product. An AE occurs on and after Study Day 1 is categorized as treatment-emergent.

Assessed by the Investigator or Sub-Investigator on the basis of his/her clinical judgment, the relationship of each AE to the investigational products are categorized as **Related** and **Not Related**.

Determined by Investigator or Sponsor, an AE will be categorized as Related to study treatment, if an AE follows a reasonable temporal sequence from investigational product administration and cannot be reasonably explained by the subject's clinical state or other factors.

#### 9.1.2. Analysis of Adverse Events

Tables summarizing the incidence of AEs will be categorized by SOC and PT, for each of the following:

- All AEs;
- Treatment-emergent AEs;
- Treatment-emergent AEs related to study treatment;
- Treatment-emergent AEs by severity;
- Treatment-emergent AEs related to study treatment by severity;
- All serious treatment-emergent AEs;
- Serious treatment-emergent AEs related to study treatment;
- AEs leading to study treatment discontinuation;
- Deaths

If subject experiences the same AE more than once with different severity (mild, moderate, and severe), then the event with the highest severity will be tabulated in "by severity" tables. If a subject experienced multiple TEAEs under the same PT (or SOC), then the subject will be counted only once for that PT (or SOC).

In summary tables, TEAEs are sorted by alphabetical order of system organ class, and then descending frequencies of preferred term within all subjects exposed to LC350189.

### 9.2. Clinical Laboratory Evaluations

Clinical laboratory results include:

- Hematology: red blood cell (RBC) count, white blood cell (WBC) count with differential (neutrophils, lymphocytes, monocytes, eosinophils, basophils), hemoglobin, hematocrit, platelet count, mean corpuscular volume (MCV), mean corpuscular hemoglobin (MCH), and mean corpuscular hemoglobin concentration (MCHC)
- Serum chemistry: alanine aminotransferase (ALT) or serum glutamate pyruvic transaminase (SGPT), albumin, alkaline phosphatase, aspartate aminotransferase (AST) or serum glutamic oxaloacetic transaminase (SGOT), total bilirubin, total protein, creatinine, blood urea nitrogen (BUN), creatine kinase, Gamma-glutamyl transferase,

potassium, sodium, carbon dioxide, calcium, magnesium, chloride, glucose, lactate dehydrogenase (LDH), phosphorus, and serum uric acid (sUA)

- Urinalysis: qualitative, appearance, color, pH, specific gravity, ketones, protein, glucose, nitrate, urobilinogen, and blood
- Serology (only at screening): HBsAg, anti-HCV, anti-HIV-1/2

Clinical laboratory values from laboratories will be graded according to CTCAE Version 4.03 for following analytes programmatically. For laboratory values that do not fall in the grade criteria of CTCAE Version 4.03, a state of ‘Normal’ will be assigned. In addition, normal ranges will be used to determine the categories of High, Low, and Normal for laboratory tests that have no severity grade.

|                                    |                                |
|------------------------------------|--------------------------------|
| Alanine Aminotransferase (Serum)   | Magnesium (Serum)              |
| Albumin (Serum)                    | Potassium (Serum)              |
| Alkaline Phosphatase (Serum)       | Sodium (Serum)                 |
| Aspartate Aminotransferase (Serum) | Hemoglobin (Blood)             |
| Bilirubin (Serum)                  | Leukocytes (Blood)             |
| Calcium (Serum)                    | Lymphocytes (Blood)            |
| Creatine Kinase (Serum)            | Neutrophils, Segmented (Blood) |
| Creatinine (Serum)                 | Platelets (Blood)              |
| Glucose (Serum Fasting)            |                                |

Descriptive statistics of baseline value, post-baseline value by visit, and change from baseline will be summarized by visit, for laboratory tests with continuous values.

Shift table representing the shift in status from baseline (e.g. positive and negative) to each visit will be produced for laboratory test with categorical values.

In addition, shift table representing the shift from baseline grade (per CTCAE criteria) to the most severe post-baseline grade for all applicable laboratory tests, and shift table representing the shift from baseline category (High, Normal, and Low) to the worst post-baseline category for laboratory test based on normal ranges of local laboratories.

Listings of clinical laboratory data with CTCAE grades or flags of abnormalities will be provided by test and subject for applicable tests.

Pregnancy test results will be listed.

